 4. 	3.1. 3.2. 3.3. 3.4.	STIGATION PLAN Study Design Comprehension Testing Physician Survey 3.3.1. Screening Phase 3.3.2. Assessment Phase Study Population 3.4.1. Physicians prescribing anti-epileptic drugs 3.4.2. Inclusion criteria for Physician Survey 3.4.3. Exclusion criteria for Physician Survey 3.4.4. Methods of Recruitment Survey Design 3.5.1. Questionnaire Structure 3.5.2. Measures to minimise bias in the surveys Physicians Screening and Assessment Physicians Outcomes	10111213131314141415
5.		COLLECTION AND MANAGEMENT	
6.	DATA 6.1. 6.2.	ANALYSISAnalysis PopulationAnalyses	16
7.	PREC	CISION BY SAMPLE SIZE	17
8.	STUD	Y LIMITATIONS	17
9.	STUD 9.1. 9.2.	OY MANAGEMENT Ethical Committee approval and consent Reporting of adverse events	18

2014N191555 ₋	_00
PRJ22	250

	9.3.	Study reporting and publications	18
10.	APPE	NDICES	19

LIST OF ABBREVIATIONS

AE Adverse Event AED Anti-epileptic drug

DHCP Dear Healthcare Professional

EU European Union

EDC Electronic Data Capture

GSK GlaxoSmithKline HCP Healthcare Profession

HCP Healthcare Professional PI Prescribing Information

REMS Risk Evaluation and Mitigation Strategy

RMP Risk Management Plan

SmPC Summary of Product Characteristics
UBC United BioSource Corporation

UK United Kingdom

US United States of America

Trademark Information

Trademarks of the GlaxoSmithKline group of companies	Trademarks not owned by the GlaxoSmithKline group of companies
TROBALT	

PROTOCOL SUMMARY

Rationale

The European Risk Management Plan (RMP) describes the measures taken by GlaxoSmithKline (GSK), the maker of TROBALTTM (retigabine) – later referred to TROBALT, to communicate the identified risks associated with TROBALT. As part of this RMP, GSK will conduct a survey of physicians' understanding of specific risks associated with TROBALT (retigabine), as described in the Prescribing Information (PI) and communicated to health care professionals. The goal of the survey is to assess prescriber awareness of label changes for retigabine and evaluate the effectiveness of the communication of recognised risks related to use of TROBALT in 11 European markets and Hong Kong.

The results of this survey will be used to inform GSK as to whether any additional measures are needed to help ensure appropriate use of the product.

Objective(s)

The objective of this study is to assess prescribers' awareness of recent label changes, including the appropriate patient population related to TROBALT as evaluated by a survey instrument.

Study Design

This is a cross sectional survey of a targeted sample of 1000 physicians:

- who have prescribed an anti-epileptic drug (AED) at least once in the last 6 months, and
- who were sent a Dear Healthcare Professional (DHCP) letter in June 2013, and
- who practice in one of the following 12 countries (Austria, Belgium, Bulgaria, France, Hong Kong, Italy, Norway, Poland, Slovakia, Spain, Switzerland and the United Kingdom).

The study will consist of two parts:

- (1) Comprehension Testing (sample in UK only) to determine if the survey instrument is clear and questions are understood, and
- (2) the online Physician Survey.

The Comprehension Testing will be conducted among a group of 16 physicians in the UK to evaluate the draft survey instrument and study procedures prior to rolling out the

Physician Survey in 12 countries. A full description of the Comprehension Testing has been detailed in a separate qualitative research plan including a description of the research methodology and the physician sample to be recruited. The findings from the Comprehension Testing will serve as the basis for whether or not any modifications need to be made to the survey instrument.

The Physician Survey will be conducted in two phases: Screening Phase and Assessment Phase.

The Screening Phase of the survey will include up to 1000 potential prescribers of TROBALT (i.e. those who have prescribed any AED within the past 6 months) in order to reach a target sample of 200 prescribers and 200 non-prescribers assuming a recruitment failure of 60%.

The respondents will be asked several questions to obtain information on their medical specialty, country in which they practice, AED prescribing history, and whether they have prescribed TROBALT. Respondents, who have prescribed TROBALT, and a sample of those who have not prescribed TROBALT, will be asked to take part in the Assessment Phase of the survey.

The purpose of the Assessment Phase of the survey is to evaluate respondents' understanding of the risks associated with TROBALT. There will be approximately 200 prescribing physicians who have prescribed TROBALT included in the study across the following countries: Austria, Belgium, Bulgaria, France, Hong Kong, Italy, Norway, Poland, Slovakia, Spain, Switzerland and the United Kingdom. Additionally, there will be up to 200 prescribing physicians who have never or not recently prescribed TROBALT selected from all countries.

Study Assessments

The outcome of the survey is the proportion of physicians providing correct responses to a series of questions concerning specific risks associated with TROBALT. Additional analyses will compare the level of understanding between physicians who have prescribed TROBALT and those who have never or not recently prescribed the product. The specific risks evaluated will be from those listed in section 4.2.

1. INTRODUCTION

GlaxoSmithKline (GSK) will conduct a survey of physicians who are prescribing epileptic drugs (AEDs) to determine their understanding of specific TROBALT. The target physicians to be surveyed in each country will who have received a Dear Healthcare Professional (DHCP) letter (

Appendix 1) sent in June 2013. The survey will concentrate on risks described in the product label for TROBALT, as revised on 31st May 2013. It is recognised that the DHCP letter and TROBALT Prescribing Information (PI) are not the only source of information concerning risks associated with medication use available to the prescriber.

The design for this study is based on GSK's previous experience designing risk management programs for GSK products, and on the prior experience of United BioSource Corporation (UBC) in conducting similar surveys in the European Union (EU).

The results of this survey will be used to inform GSK as to whether any additional measures are required to optimise the benefit/risk profile for retigabine.

2. OBJECTIVE

The objective of this study is to assess prescribers' awareness and knowledge of the management of specific risks associated with TROBALT and the appropriate patient population as evaluated by a survey instrument.

3. INVESTIGATION PLAN

3.1. Study Design

This study is sponsored by GSK, and will be conducted by United BioSource Corporation (UBC), an international research consultancy.

Physicians will be recruited by selecting a random sample from lists provided by each country. The list includes names of all potential AED DHCP letter (

Appendix 1). Following recruitment, physicians' understanding of the potential risks associated with TROBALT will be evaluated using an online survey. Each invitation will include information on how to access the survey on-line, and will include a unique code to ensure that the invitation is used only once.

To ensure comprehension of the survey invitation and the survey questions, all of the physician outreach will be conducted in the local country language. Specifically, the surveys and invitation letters will all be translated by a certified translation company.

The study will consist of two parts: Comprehension Testing of the draft survey with a small group of physicians to be sure the questions and response options are understood and the Physician Survey which is a cross-sectional survey of physicians across 12 countries.

3.2. Comprehension Testing

The purpose of the Comprehension Testing is to evaluate draft questions to be used in the Physician Survey instrument in approximately 16 subjects. Survey questions will be designed to assess physician understanding of specific risks associated with TROBALT.

Structured physician one-to-one in-depth telephone interviews will yield qualitative findings and will help provide the basis for the development of the survey. Revisions to the questionnaire or to study procedures will be made before administration of the main survey.

The survey instrument used for the Comprehension Testing will be revised based on physician responses before being fielded for the main study. The survey instrument will be developed in English and then later translated into relevant languages for the other participating countries.

3.3. Physician Survey

The physician survey will be conducted in two phases: Screening Phase and the Assessment Phase. This cross-sectional study has been designed to assess prescribers' understanding of the appropriate patient population to treat with TROBALT and the new safety monitoring activities that have been instituted.

The selected countries are the eight largest markets in the EU based on estimated number of patients receiving TROBALT (the United Kingdom, Spain, France, Italy, Belgium, Slovakia, Poland and Austria). One additional EU country (Bulgaria) was selected upon the potential uncertainty related to reimbursement of an ophthalmology exam mandated by the TROBALT PI. Three non-EU countries (Switzerland, Hong Kong and Norway) were selected to represent markets where TROBALT is available outside the EU.

3.3.1. Screening Phase

The Screening Phase seeks to survey physicians to identify the proportion of physicians who have prescribed TROBALT and to summarize the type of medical specialty of those physicians with experience in prescribing TROBALT.

Up to 1000 physicians will be invited to take part, by selecting a random sample of prescribers of AEDs from those who were sent a DHCP letter. Assuming a recruitment failure of 60%, this will permit a target sample of 200 prescribers and 200 non-prescribers to be achieved.

The survey will be composed of multiple choice and close-ended questions. There will be no open-ended questions included.

The electronic data capture (EDC) system will be configured to allow those physicians identified by their responses to the survey in the Screening Phase (Part 1) to transition into the Assessment Phase (Part 2). The EDC system will allow the first 200 physicians who indicate they have prescribed TROBALT since July 2013 to continue to Part 2 and will also limit to 200 the number of non-prescribers who are asked to complete the additional questions in Part 2.

[figure not shown]

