3.3.2. Assessment Phase

[figure not shown]
The Assessment Phase is the main part of the Physician Survey. In addition to the TROBALT prescribers, the Assessment Phase will include up to 200 respondents from the Screening Phase who have not prescribed TROBALT in order to evaluate the general awareness to the risks associated with TROBALT. The Assessment Phase will evaluate each physician's understanding of specific risks associated with TROBALT use.

The outcome of this study is the proportion of the physicians/epilepsy specialists that correctly respond to individual survey questions. The proportion responding correctly will be tabulated separately for each item.

Physician demographic information will be collected in order to further characterise the respondent population. This will include country, type of medical practice, and number of patients with epilepsy treated. The country in which practice occurs will be collected at the beginning of the survey in order to ensure a sample of respondents from each included country.

At the conclusion of the online survey, the final computer screen will display a summary of the relevant sections from the country-specific Prescribing Information to allow the physician access to the full TROBALT label, to ensure they have a reminder and full understanding of the safety revisions that were implemented in 2013.

^{*} In case of a very low response, known prescribers will be specifically invited to participate. Such enrichment of the sample is not anticipated to bias the outcomes as the targeted physicians will also be DHCP recipients and will need to fulfil inclusion criteria.

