3.4. Study Population

3.4.1. Physicians Prescribing Anti-Epileptic Drugs

This survey aims to recruit a random sample of 1000 physicians prescribing AEDs and who have been sent a DHCP letter in Austria, Belgium, Bulgaria, France, Hong Kong, Italy, Norway, Poland, Slovakia, Spain, Switzerland and the United Kingdom.

The selected countries are the eight largest markets in the EU for TROBALT use based on estimated number of patients receiving TROBALT (the United Kingdom, Spain, France, Italy, Belgium, Slovakia, Poland and Austria). One additional EU country (Bulgaria) was selected upon the potential uncertainty related to reimbursement of an ophthalmology exam mandated by the TROBALT PI. Three non-EU countries (Hong Kong, Norway and Switzerland) were selected to represent markets where TROBALT is available, outside the EU.

If required, additional countries may be included in the survey to reach the minimum recruitment target. The recruitment will be from among those who have prescribed an anti-epileptic drug at least once in the last 6 months, and who were on the list to which a DHCP letter was distributed in June 2013. The survey will aim to recruit at least 200 physicians (from the 12 specified countries) prescribing TROBALT for sub-analyses, as these individuals would be expected to be more aware of the risks of TROBALT, and up to 200 physicians not prescribing TROBALT as a comparison.

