3.5.2. Measures to Minimise Bias in the Surveys

The following are measures to minimise bias in the surveys:

- 1. All questions will be programmed to ensure that questions are asked in the appropriate sequence. Skip patterns will be clearly indicated. Respondents cannot go back to a question once the question has been answered and cannot skip ahead. All questions must be answered in order to complete the survey.
- 2. Response options presented in a list will be randomized to minimize positional bias.
- 3. Comprehension Testing will be conducted among 16 physicians in the UK to evaluate the draft survey questions and to assess the questions understanding and whether proper wording has been used prior to the survey being implemented to the full sample.

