4.2. Physicians Outcomes

Physicians understanding of specific risks and the appropriate patient population related to TROBALT will be assessed using a standardised questionnaire.

The outcome of this study is the proportion of physicians that correctly respond to individual survey questions concerning risks associated with TROBALT. The proportion responding correctly will be tabulated separately for each item in the physician understanding survey instrument. The risks that will be evaluated in the survey are listed below:

- 1. Pigment changes (discolouration) of ocular tissues, including the retina
- 2. Pigment changes (discolouration) of the nails, lips and/or skin
- 3. Urinary retention (generally within the first 8 weeks of treatment)
- 4. Psychotic disorders (including confusional state and hallucinations)

^{*}Used to ensure that the sample includes at least 200 TROBALT prescribers

5. QTc prolongation.

Physician demographic information will be collected in order to further characterise the respondent population. This will include country, type of medical practice, and number of patients with epilepsy treated.

At the conclusion of the online survey, the final computer screen will display a summary of the relevant information from the country-specific Prescribing Information, which can be printed for reference to allow the physician access to the full TROBALT label to ensure they have a reminder and full understanding of the safety revisions that were implemented in 2013.

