6. DATA ANALYSIS

6.1. Analysis Population

The population for analysis will comprise all physicians recruited into the study, meeting eligibility criteria as assessed in the survey screener, and completing the survey.

The outcomes will be summarised for all 12 specified countries combined.

The two sub-populations for analyses will be 1) the physicians who have prescribed TROBALT after receiving a DHCP letter in June 2013, and 2) the physicians who have prescribed TROBALT in the past, but before receipt of the DHCP letter or the physicians who have never prescribed TROBALT.

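### The 200-prescriber quota is a ceiling counted at entry to Part 2, while the protocol wants at least 200 and analyses only completers, so any break-off leaves fewer than 200

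*Protocol*

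**What the plan says.** The protocol describes the prescriber number in three ways.

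- **Ceiling at entry.** Section 3.3.1: "The EDC system will allow the first 200 physicians who indicate they have prescribed TROBALT since July 2013 to continue to Part 2". The same sentence tells the system to "limit to 200 the number of non-prescribers who are asked to complete the additional questions in Part 2".
- **Floor.** Section 3.4.1: "The survey will aim to recruit at least 200 physicians (from the 12 specified countries) prescribing TROBALT for sub-analyses". The same sentence gives non-prescribers only an upper limit of 200, so the two groups are treated differently on purpose. The footnote to the screening questions of section 4.1 (printed within 4.2) repeats the floor: "Used to ensure that the sample includes at least 200 TROBALT prescribers".
- **Approximate number.** Protocol Summary, Study Design: "There will be approximately 200 prescribing physicians who have prescribed TROBALT included in the study".

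Two sections settle who counts. Section 3.4.4 continues reminders until enough surveys have been completed. Section 6.1 restricts the analysis population to eligible recruits "meeting eligibility criteria as assessed in the survey screener, and completing the survey". Section 3.5.2 defines completion strictly: "All questions must be answered in order to complete the survey".

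**The concern.** The gate counts physicians who enter Part 2, whereas the target and the analysis count physicians who finish it. Anyone who enters and stops has used a quota place and contributes nothing. The text does not reopen the gate, replace a break-off or use partial answers.

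The remedies that the protocol does provide all act before the gate: reminders, invitations to known prescribers if response is very low, and additional countries. Once 200 prescribers have entered, a physician brought in by any of them would be turned away. Section 3.4.4 would then be pursuing a number of completes that section 3.3.1 prevents.

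At stake are the size of the prescriber subgroup, which section 3.4.1 wants for the sub-analyses, and the answers of those who stop. Those answers are dropped even for items already answered, and could differ from the answers of completers.

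**Working it through.** **Inputs from the protocol.** Entry cap 200 per group (3.3.1); prescriber floor 200 (3.4.1 and the 4.1 footnote); 1000 invited with 60% recruitment failure (3.3.1); 95% confidence and 60% correct (worked example in section 7). **Assumed:** break-off rate *b* within Part 2, range 1% to 20%, because the protocol gives none.

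**Step 1: the plan's own figures.** Invitations: 1000 × (1 − 0.60) = 400 = 200 + 200, as stated. Section 7 gives ±7.0 points for n = 200 at 60% correct.

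- Wald: 1.96 × √(0.60 × 0.40 / 200) = 6.79 points.
- Wald with continuity correction: 6.79 + 100 × 0.5/200 = 7.04 points.
- Exact (Clopper-Pearson, 120 of 200): interval 52.85% to 66.85%, half-width 7.00 points.

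The stated figure reproduces. The 60% allowance sets the number of invitations; it does not change the entry cap.

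**Step 2: what the cap permits.** Completers ≤ entrants ≤ 200. At least 200 completers is therefore possible only if all 200 entrants finish. If break-offs are independent, the chance of that is (1 − b)^200: 13% at b = 1%, 1.8% at 2%, and about 0.004% at 5%.

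**Step 3: size of the shortfall.** Expected completers = 200 × (1 − b). Entry cap needed for an expected 200 completers = 200 / (1 − b), rounded up. Margins are half-widths at 60% correct.

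| Assumed b | Completers | Wald margin (points) | Exact margin (points) | Entry cap needed |
|---|---|---|---|---|
| 0% | 200 | 6.79 | 7.00 | 200 |
| 5% | 190 | 6.97 | 7.18 | 211 |
| 10% | 180 | 7.16 | 7.39 | 223 |
| 20% | 160 | 7.59 | 7.84 | 250 |

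Either method gives a loss of about 0.2, 0.4 and 0.8 points.

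**Step 4: discarded break-offs.** For any item, the completers' proportion minus the all-entrant proportion equals b × (proportion correct in completers − proportion correct in break-offs). The protocol gives neither factor, so neither the sign nor the size can be fixed.

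**The case against.** **The floor may concern recruitment.** Section 3.4.1 speaks of an aim to recruit, and 200 admitted physicians could be said to meet it; the Summary's wording is looser still. The sponsor may also have meant a quota on completes, as section 3.4.4 suggests. This is fair as to intent. But the 200 are wanted for sub-analyses, only completers are analysed, and section 3.3.1 as written tells a programmer to count entrants.

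**The cap may never bind.** On the protocol's own assumptions exactly 200 prescribers arrive, and section 8 expects low numbers per country. This stands: if fewer than 200 prescribers enter, the cap does no harm. A reader might infer that scarce prescribers will be turned away or that the target is bound to be missed. The documents support neither; with no break-offs, exactly 200 would be analysed.

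**The precision loss is small.** This stands. The Wald margin of 7.0 at n = 190 looks the same as the ±7.0 stated for n = 200, but on the exact method the comparison is 7.00 with 7.18. Either way the change is minor.

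**Inflated results.** A reader might assume 60% correct in completers and 40% in break-offs, and conclude that the reported figure is 1, 2 or 4 points too high at 5%, 10% or 20% break-off. That contrast has no source. Physicians may stop for lack of time as readily as for lack of knowledge. A completers-only population is also an explicit and legitimate choice.

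**Country balance.** Section 3.3.2 collects country at the start "in order to ensure a sample of respondents from each included country", and a reader might want a hard country limit on the first-come gate. Section 3.4.4 already monitors response by country, section 8 pools all countries, and a hard limit could itself exclude respondents. The case for one is not made.

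**Conclusion.** The concern holds as an inconsistency within the protocol. The prescriber quota is a ceiling counted on entrants, while the stated target is a floor (or an approximate figure) and the analysis counts completers. The analysable prescriber group is therefore at most 200, and below 200 after any break-off once the gate has closed.

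The consequence is modest: about 0.2 to 0.8 points of margin for assumed break-off of 5% to 20%. This rests on the gate filling and on section 3.3.1 being implemented literally. The flow figures in 3.3.1 and 3.3.2 could not be read; if they show a quota on completes, the text still needs to agree with them. Selection bias from dropping break-offs is possible but cannot be quantified from the documents.

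**What to change.** 1. In section 3.3.1, count the prescriber quota on completed surveys, or remove the prescriber cap. Count the 200 limit for non-prescribers on completes as well.
2. Use one statement of the prescriber target in the Protocol Summary, 3.3.1, 3.4.1 and the footnote to 4.1, and say that it refers to completed surveys.
3. As a secondary step, report the number of break-offs in each group and add a supportive per-item analysis that includes the answers given before stopping. Section 3.5.2 does not allow a respondent to return to an answered question, so these answers are final. Later items are not recovered, so this only partly addresses possible selection. Completers can remain the main population.

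The cost is a system setting and a few lines of text, possibly a few extra £60 honoraria if more than 200 prescribers complete, and denominators that differ slightly by item in the supportive analysis. Steps 1 and 2 belong before fielding, because the protocol provides no way back for a prescriber turned away at the gate.
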